#### **4.5.1.7 CI score at Week 6 and Week 12**

At each post-baseline visit, the CI score will be analyzed using an ANCOVA model with treatment group, gender, denture material type (acrylic or cobalt chrome), and baseline mean overall MGI score (low, high) as factors and the baseline CI score as a covariate. The adjusted means and SEs of the two treatment groups together with the treatment difference, SE, 95% confidence interval of the difference and between-group p-value will be provided in [Table 14.2.8.1.2](#) for the mITT population.

Descriptive statistics (n, mean, SD, SE, median, minimum, maximum) of the CI score will be provided at Baseline, Week 6 and Week 12 visits by treatment group (and overall for Baseline only) for the mITT population ([Table 14.2.8.1.1](#)).

The raw mean and SE of the CI score (whole mouth and associated with abutment teeth) will be presented graphically over time for each treatment group in [Figure 14.2.6](#) (mITT population).

The CI value obtained for each tooth and surface will be listed by subject and visit in [Listing 16.2.6.5](#) for all randomized subjects. The CI score will be listed by subject and visit in [Listing 16.2.6.6.2](#) for all randomized subjects.

#### **4.5.1.8 ODI score at Week 6 and Week 12**

At each post-baseline visit, the ODI score will be analyzed using an ANCOVA model with treatment group, gender, denture material type (acrylic or cobalt chrome), and baseline mean overall MGI score (low, high) as factors and the baseline ODI score as a covariate. The adjusted means and SEs of the two treatment groups together with the treatment difference, SE, 95% confidence interval of the difference and between-group p-value will be provided in [Table 14.2.9.1.2](#) for the mITT population.

Descriptive statistics (n, mean, SD, SE, median, minimum, maximum) of the ODI score will be provided at Baseline, Week 6 and Week 12 visits by treatment group (and overall for Baseline only) for the mITT population ([Table 14.2.9.1.1](#)).

The raw mean and SE of the ODI score (whole mouth and associated with abutment teeth) will be presented graphically over time for each treatment group in [Figure 14.2.7](#) (mITT population).

The ODI value obtained for each tooth and surface will be listed by subject and visit in [Listing 16.2.6.5](#) for all randomized subjects. The ODI score will be listed by subject and visit in [Listing 16.2.6.6.2](#) for all randomized subjects.

#### **4.5.1.9 OHI score at Week 6 and Week 12**

At each post-baseline visit, the OHI score will be analyzed using an ANCOVA model with treatment group, gender, denture material type (acrylic or cobalt chrome), and baseline mean overall MG1 score (low, high) as factors and the baseline OHI score as a covariate. The adjusted means and SEs of the two treatment groups together with the treatment difference, SE, 95% confidence interval of the difference and between-group p-value will be provided in [Table 14.2.10.1.2](#) for the mITT population.

Descriptive statistics (n, mean, SD, SE, median, minimum, maximum) of the OHI score will be provided at Baseline, Week 6 and Week 12 visits by treatment group (and overall for Baseline only) for the mITT population ([Table 14.2.10.1.1](#)).

The raw mean and SE of the OHI score (whole mouth and associated with abutment teeth) will be presented graphically over time for each treatment group in [Figure 14.2.8](#) (mITT population).

The OHI score will be listed by subject and visit in [Listing 16.2.6.6.2](#) for all randomized subjects.

#### **4.5.2 Efficacy (Exploratory)**

With the exception of the cleaning perceptions questionnaire, each exploratory variable will be analyzed in a similar manner as described for the primary and secondary endpoints ([Section 4.4.1.2](#) and [Section 4.5.1](#)). All analyses will be conducted on the mITT population only. For all of the exploratory analyses, normality assumptions in ANCOVA models will be checked and accounted for in the same way as for the primary variable.

#### **4.5.2.1 Cleaning Perceptions Questionnaire scores at Week 6 and Week 12**

For the cleaning perceptions questionnaire, frequency count (n) and percentages (%) will be provided for each question and response category by treatment group for baseline (overall for Baseline only) for the mITT population ([Table 14.2.11.1](#)). Simillary Q12 to Q18 will be presented in [Table 14.2.11.2](#) by visit and treatent group, in addition, the mean general oral care confidence (n, mean, SD, median, minimum and maximum) with t-test (mean difference, 95 % CI and p-value ) will be presented for Week 6 and Week 12.

A treatment comparison also will be performed by using Cochran Mantel-Haenszel test on Q12 to Q18 and p-value will be presented for Week 6 and Week 12 in [Table 14.2.11.2](#).

The results of the cleaning perceptions questionnaire will also be listed ([Listing 16.2.6.8](#)).

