### **3.2 Subgroups/Stratifications**

Eligible subjects will be stratified based on denture material type (acrylic or cobalt chrome) and baseline mean overall MGI score (Low:  $\leq 2.0$ /High:  $> 2.0$ ) to ensure a balance in treatments across the strata, and then randomized into one of two treatment groups (Intervention Group/No Intervention Group).

There will be four strata according to denture material type (acrylic or cobalt chrome) and baseline mean overall MGI score (Low:  $\leq 2.0$ /High:  $> 2.0$ ):

- Stratum 1: Denture material is acrylic, Baseline MGI  $\leq 2.0$
- Stratum 2: Denture material is acrylic, Baseline MGI  $> 2.0$
- Stratum 3: Denture material is cobalt chrome, Baseline MGI  $\leq 2.0$
- Stratum 4: Denture material is cobalt chrome, Baseline MGI  $> 2.0$

The primary and secondary analysis will include gender (Male/Female), denture material type (acrylic or cobalt chrome) and mean baseline MGI (Low:  $\leq 2.0$ /High:  $> 2.0$ ) as factors, with the exception of the analysis of MGI, for which the stratification factor of MGI will not be included as the baseline value of MGI will be included as a covariate.

No subgroup analyses are planned for this study.

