#### **4.4.3 Exploratory Efficacy Variables**

##### **4.4.3.1 Cleaning Perceptions Questionnaire scores at Week 6 and Week 12**

The cleaning perceptions questionnaire will be completed at Baseline (Visit 2), Week 6 (Visit 3) and Week 12 (Visit 4) to evaluate subject's perceptions of dental/denture cleaning.

The questionnaire consists 5 questions relating to general oral care and 2 questions relating to oral care routine.

At Baseline the questions will be scored from 1 to 4 (with a response of 1 indicating not at all confident/motivated/likely and a response of 4 indicating very confident/motivated/likely).

At Week 6 and Week 12 the questions will be in comparison to the period before the subject begins this study and will be scored from 1 to 5 (with a response of 1 indicating a lot less confident/motivated/likely, a response of 3 indicating no difference and a response of 5 indicating a lot more confident/motivated/likely).

The mean general oral care confidence at Week 6 and at Week 12 will be derived for each subject as the average score of question 12 to question 16.

At Baseline, 4 additional questions relating to the subject's attitude to oral care will be completed.

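### The questionnaire t-test is unadjusted although randomisation is stratified, and the CMH strata and statistic for Q12–Q18 are not specified

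*SAP*

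**What the plan says.** SAP 4.5.2.1 plans two kinds of between-arm test on the questionnaire, each at Weeks 6 and 12.

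- **Mean general oral care confidence (mean of Q12 to Q16).** This is summarised "with t-test (mean difference, 95 % CI and p-value ) will be presented for Week 6 and Week 12". No factor or covariate is named.
- **Single items.** "A treatment comparison also will be performed by using Cochran Mantel-Haenszel test on Q12 to Q18", with a p-value at each visit. The text does not say whether the test is stratified, or which statistic of the CMH family is meant.

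SAP 3.2 describes the randomisation: "Eligible subjects will be stratified based on denture material type (acrylic or cobalt chrome) and baseline mean overall MGI score", which gives four strata. It then sets the adjustment rule: "The primary and secondary analysis will include gender (Male/Female), denture material type (acrylic or cobalt chrome) and mean baseline MGI" category as factors, with the MGI category left out when MGI itself is analysed. SAP 4.5.2 takes this endpoint out of the ANCOVA approach: "With the exception of the cleaning perceptions questionnaire, each exploratory variable will be analyzed in a similar manner" to the primary and secondary endpoints. It gives no reason.

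SAP 4.4.3.1 describes the instrument. "At Baseline the questions will be scored from 1 to 4", as an absolute rating. At Weeks 6 and 12 the scale runs from 1 to 5 and asks for a comparison with the time before the study, with 3 meaning no difference. The mean confidence score is derived at Weeks 6 and 12 only.

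Protocol 12.2.8 classes the endpoint as exploratory, plans to summarise and list it, and leaves further analysis detail to the RAP.

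**The concern.** Every other between-arm efficacy comparison in the SAP is an ANCOVA with at least gender, denture material and the endpoint's own baseline value. The questionnaire comparison of means adjusts for nothing.

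When allocation is balanced within strata, the true sampling variance of the treatment difference no longer contains the between-stratum component. An unadjusted t-test still puts that component into its standard error. Its interval is then wider than the design warrants, and its p-value is on average too large.

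The CMH issue is one of specification. With two arms, the correlation and row-mean-scores statistics have 1 df, while general association has up to 4 df on five response categories. Two programmers could follow the text, report different p-values for seven items at two visits (14 tests), and both comply. Q12 to Q18 are ordered responses and the question is directional, so the choice affects power. It should be fixed before the data are unblinded.

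**Working it through.** The documents give no effect size, SD, power or error rate for the questionnaire, so there is no stated figure to reproduce. What follows is illustrative.

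**Inputs from the documents**
- About 128 evaluable subjects (SAP 1.4), equally allocated (Protocol 5.1), so 64 per arm.
- Four randomisation strata (SAP 3.2).
- Five ordered response categories at follow-up (SAP 4.4.3.1).

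**Assumptions**
- Two-sided 0.05. Protocol section 3 states this level for the Bleeding Index only.
- Standardised difference d = 0.5.
- Strata and baseline answer each explain 2%, 10% or 20% of the variance of the mean score.

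**1. Formula check.** Power = Φ(d / √(2(1 − R²)/64) − 1.96), where R² is the share of variance removed by adjustment. At R² = 0 this is Φ(0.5/0.1768 − 1.96) = Φ(0.868) = 80.7%. At R² = 0.02, 0.05, 0.10, 0.20 and 0.30 it is 81.5%, 82.7%, 84.6%, 88.5% and 92.2%. For d = 0.3 the range from R² = 0 to 0.30 is 39.6% to 52.7%.

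**2. Simulation under stratified allocation.** There were 8,000 trials per setting, with N = 128, four strata, exact balance within strata and a normal outcome. Gender was not modelled.

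| Variance explained by strata / by baseline answer | Type I error, t-test | Power, t-test | Power, strata | Power, strata + baseline |
|---|---|---|---|---|
| 2% / 2% | 4.9% | 80.5% | 81.1% | 81.4% |
| 10% / 10% | 3.6% | 81.8% | 84.5% | 88.2% |
| 20% / 20% | 3.3% | 83.0% | 88.3% | 95.2% |

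- Gain over the t-test from strata and baseline together: 81.4 − 80.5 = 0.9, 88.2 − 81.8 = 6.4 and 95.2 − 83.0 = 12.2 points.
- Gain from strata alone: 0.6, 2.7 and 5.3 points.
- Type I error of the adjusted models was 4.7% to 5.6%. The Monte Carlo standard error at 5% is √(0.05 × 0.95/8000) = 0.24 points.
- Large-sample check of the t-test's conservatism: the actual level is 2[1 − Φ(1.96/√(1 − R²))], with R² the share due to strata. This gives 4.8%, 3.9% and 2.8%, the same pattern as the simulation.

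**3. CMH statistic.** An ordered effect with 80% power on 1 df has noncentrality (1.96 + 0.84)² ≈ 7.85. A chi-square statistic with that noncentrality has power 80.0% on 1 df, 70.9% on 2 df, 64.5% on 3 df and 59.5% on 4 df. The 4-df figure applies when all five response categories are used. With fewer occupied categories the loss is smaller.

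**The case against.** The strongest reply is that little is at stake and no rule is broken. That largely stands.

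- **A reader might infer that the CMH test ignores the strata.** The documents do not support this. SAP 4.5.2.1 neither names nor excludes strata, and CMH is a test that can be stratified. The list of data displays in Attachment 1 is redacted, so it cannot be checked for further detail. The supported statement is that strata and statistic are unspecified. For the same reason the fall from 80% to about 60% power is conditional: the SAP does not choose general association.
- **A reader might infer that the SAP breaks its own adjustment rule.** It does not. SAP 3.2 states the rule for primary and secondary analyses, and SAP 4.5.2 expressly excepts the questionnaire.
- **A reader might treat the baseline answers as an ordinary baseline covariate, like baseline BI.** They are not. Baseline is an absolute 1–4 rating, while follow-up is a 1–5 rating of change since before the study. The follow-up score already contains a comparison with the pre-study period, a change score cannot be formed, and no baseline mean is derived. The correlation between the two is unknown.
- **Nothing in the documents shows that denture material or MGI category predicts a change in confidence.** If they do not, the t-test loses almost nothing.

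What remains is that the t-test is unadjusted as written, that the stratification factors are already in the data, and that the RAP is where the protocol placed the missing analysis detail.

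**Conclusion.** The point holds as a minor improvement. The t-test on mean confidence is valid, but under stratified allocation it is conservative to a degree that depends on how strongly the strata predict the score. The loss in power is about 1 point if strata and baseline answers each explain 2% of variance and about 6 to 12 points if each explains 10% to 20%. Strata alone account for roughly 1 to 5 of those points. All these figures rest on the assumed d = 0.5, 64 per arm and assumed variance shares, and the documents do not show which case applies.

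The CMH plan is incomplete, not wrong. If general association were used on all five categories, power would be about 60% where the 1-df statistic has 80%.

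It would be a mistake to infer inflated false positives for the t-test or a threat to the trial's conclusion. The t-test errs on the conservative side, the endpoint is exploratory, and Protocol section 3 ties study success to the Bleeding Index at 12 weeks alone.

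**What to change.** Amend SAP 4.5.2.1 before database lock.

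1. **Mean general oral care confidence.** Replace the t-test at Weeks 6 and 12 with an ANCOVA with treatment, gender, denture material and baseline MGI category (low/high) as factors. Report the adjusted difference, 95% confidence interval and p-value.
2. **Optional covariate.** The mean of the five baseline general oral care items may be added. The SAP must then define this derivation and say that it is on a different scale from the outcome. The gain is uncertain.
3. **Q12 to Q18.** State that the CMH test uses the 1-df row-mean-scores statistic, stratified by the four randomisation strata, and name the scores (1 to 5). Say what will be done if a stratum is too sparse to contribute.

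The cost is a few sentences of SAP text and changed procedure calls, a check for sparse strata, and one added derivation if the baseline covariate is used. No new data are needed.

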#### **4.5.2.2 BI score associated with abutment teeth at Week 6 and Week 12**

At each post-baseline visit, the BI score associated with abutment teeth will be analyzed using an ANCOVA model with treatment group, gender and denture material type (acrylic or cobalt chrome) factors and the baseline BI score (associated with abutment teeth) as a covariate. The adjusted means and SEs of the two treatment groups together with the treatment difference, SE, 95% confidence interval of the difference, between-group p-value and the proportionate reduction will be provided in [Table 14.2.2.3.2](#) for the mITT population.

The proportionate reduction will be calculated as:

- Proportionate reduction = [(Adjusted Mean of No Intervention Group – Adjusted Mean of Intervention Group)/Adjusted Mean of No Intervention Group]\*100.

Descriptive statistics (n, mean, SD, SE, median, minimum, maximum) of the BI score associated with abutment teeth will be provided at Baseline, Week 6 and Week 12 visits by treatment group (and overall for Baseline only) for the mITT population ([Table 14.2.2.3.1](#)).

The raw mean and SE of the BI score (whole mouth and associated with abutment teeth) will be presented graphically over time for each treatment group in [Figure 14.2.1.1](#) (mITT population).

Abutment teeth are indicated in the listing of BI ([Listing 16.2.6.1](#)). The BI score associated with abutment teeth will be listed by subject and visit in [Listing 16.2.6.7.1](#) for all randomized subjects.

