## 12.2.5 Primary Analysis

The mITT population will be used for the primary analysis. The primary efficacy endpoint will be the Bleeding Index (BI) score after 12 weeks of study treatments. The BI score will be calculated as the average index values over all tooth sites. An ANCOVA model will be used for the primary analysis with treatment, gender, denture material type (acrylic or cobalt chrome), and baseline mean overall MGI score (low, high) as factors and the baseline BI score as a covariate. The adjusted means of the two treatments, the proportionate reduction for each treatment group, and the treatment difference will be provided together with 95% CI and P-values.

The null and alternative hypotheses to be tested in the primary analyses are;

$H_0$ : There is no treatment difference in mean BI score after 12 weeks  
 $H_1$ : There is a treatment difference in mean BI score after 12 weeks

The assumption of normality and homogeneity of variance in the ANCOVA model will be investigated and if violated, data transformations will be investigated. If suitable transformations cannot be found, non-parametric tests will be performed, and results will be compared with the ANCOVA results. If the inferences from the two analyses are similar, then both sets of results will be reported and emphasis will be made on the ANCOVA results. In case of discrepancies between inferences of the ANCOVA and non-parametric analysis, results will be drawn from the non-parametric analysis.

A PP analysis will be performed on the primary analysis only if 10% or more mITT subjects are excluded from the PP population.

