### **12.2.8 Exploratory Analyses**

The following endpoints are all considered exploratory. The analysis of these endpoints will be performed in a similar manner to the primary or secondary analysis described above.

***Unless indicated otherwise, the following endpoints will be analyzed using the same ANCOVA model with mITT population as used for the primary or secondary analysis.***

- BI associated with abutment teeth at 6 and 12 weeks.
- Number of bleeding sites associated with abutment teeth at 6 and 12 weeks.
- TPI associated with abutment teeth (overall and interproximal) at 6 and 12 weeks.

- CI associated with abutment teeth at 6 and 12 weeks.
- ODI associated with abutment teeth at 6 and 12 weeks.
- OHI associated with abutment teeth at 6 and 12 weeks.
- MGI associated with abutment teeth at 6 and 12 weeks. MGI score will be calculated as the average index associated with the abutment teeth only. At each post-baseline visit, the MGI score will be analyzed using an ANCOVA model with treatment, gender and denture material type (acrylic or cobalt chrome) as factors and baseline MGI score as a covariate. As baseline MGI score is included as a covariate, baseline mean overall MGI score (low, high) is not required. Adjusted means of the two treatments, the proportionate reduction for each treatment group, and the treatment difference will be provided together with 95% CI and P-values.
- Cleaning Perceptions Questionnaire at 6 and 12 weeks will be summarized and listed. Additional details of the proposed statistical analysis will be documented in the RAP.
- RPD photographs - No analysis will be performed on these photographic images. These will be incorporated into the clinical study report for illustration of the PDCI scale only.

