#### **4.5.1.2 MGI Score at Week 6 and Week 12**

At each post-baseline visit, the MGI score will be analyzed using an ANCOVA model with treatment group, gender and denture material type (acrylic or cobalt chrome) factors and the baseline MGI score as a covariate. For the analysis of MGI the stratification factor of MGI will not be included as the baseline value of MGI is included as a covariate. The adjusted means and SEs of the two treatment groups together with the treatment difference, SE, 95% confidence interval of the difference, between-group p-value and the proportionate reduction will be provided in [Table 14.2.4.1.2](#) for the mITT population.

The proportionate reduction will be calculated as:

- Proportionate reduction =  $[(\text{Adjusted Mean of No Intervention Group} - \text{Adjusted Mean of Intervention Group}) / \text{Adjusted Mean of No Intervention Group}] * 100$ .

Descriptive statistics (n, mean, SD, SE, median, minimum, maximum) of the MGI score will be provided at Baseline, Week 6 and Week 12 visits by treatment group (and overall for Baseline only) for the mITT population ([Table 14.2.4.1.1](#)).

The raw mean and SE of the MGI score (whole mouth and associated with abutment teeth) will be presented graphically over time for each treatment group in [Figure 14.2.3](#) (mITT population).

The MGI value obtained for each tooth, surface and site will be listed by subject and visit in [Listing 16.2.6.2](#) for all randomized subjects. The MGI score will be listed by subject and visit in [Listing 16.2.6.6.1](#) for all randomized subjects.

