#### **4.5.2.3 Number of bleeding sites associated with abutment teeth at Week 6 and Week 12**

At each post-baseline visit, number of bleeding sites associated with abutment teeth will be analyzed using an ANCOVA model with treatment group, gender, denture material type (acrylic or cobalt chrome), and baseline mean overall MGI score (low, high) as factors and the baseline number of bleeding sites (associated with abutment teeth) as a covariate. The adjusted means and SEs of the two treatment groups together with the treatment difference, SE, 95% confidence interval of the difference, between-group p-value and the proportionate reduction will be provided in [Table 14.2.3.2.2](#) for the mITT population.

The proportionate reduction will be calculated as:

- Proportionate reduction = [(Adjusted Mean of No Intervention Group – Adjusted Mean of Intervention Group)/Adjusted Mean of No Intervention Group]\*100.

Descriptive statistics (n, mean, SD, SE, median, minimum, maximum) of the number of bleeding sites associated with abutment teeth will be provided at Baseline, Week 6 and Week 12

visits by treatment group (and overall for Baseline only) for the mITT population ([Table 14.2.3.2.1](#)).

The raw mean and SE of the number of bleeding sites (whole mouth and associated with abutment teeth) will be presented graphically over time for each treatment group in [Figure 14.2.2](#) (mITT population).

The number of bleeding sites associated with abutment teeth will be listed by subject and visit in [Listing 16.2.6.7.1](#) for all randomized subjects.

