### **5 Changes to the Protocol Defined Statistical Analysis Plan**

Any changes from the originally planned statistical analysis specified in the protocol are outlined in [Table 5-1](#).

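### SAP 4.5.2.2 drops the baseline-MGI stratum from the abutment-teeth BI model, contrary to Protocol 12.2.8 and without a Table 5-1 entry

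*SAP*

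**What the plan says.** Protocol 12.2.8 sets the rule for exploratory endpoints: "Unless indicated otherwise, the following endpoints will be analyzed using the same ANCOVA model with mITT population as used for the primary or secondary analysis". The list beneath it has the plain entry "BI associated with abutment teeth at 6 and 12 weeks", with no exception attached. The only endpoint there with its own reduced ANCOVA is abutment MGI, and the reason given is that baseline MGI already enters as the covariate.

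The BI model in Protocol 12.2.5 has treatment, gender and denture material, "and baseline mean overall MGI score (low, high) as factors and the baseline BI score as a covariate". Protocol 12.2.6.5 applies the same model at Week 6, and SAP 4.4.1.2 repeats it for the primary analysis.

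For abutment BI, SAP 4.5.2.2 says that "the BI score associated with abutment teeth will be analyzed using an ANCOVA model with treatment group, gender and denture material type", with baseline abutment BI as covariate. It does not mention the MGI factor. The SAP's general statement for exploratory endpoints (4.5.2) is that "each exploratory variable will be analyzed in a similar manner as described for the primary and secondary endpoints". The next section, 4.5.2.3 on abutment bleeding sites, does include the factor: "and baseline mean overall MGI score (low, high) as factors and the baseline number of bleeding sites (associated with abutment teeth) as a covariate".

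SAP section 5 describes its change log in these terms: "Any changes from the originally planned statistical analysis specified in the protocol are outlined in" Table 5-1.

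**The concern.** The protocol and SAP specify different models for the same endpoint at two visits, and nothing shows that the difference was intended. Anyone who produces Table 14.2.2.3.2 from the SAP will fit a model the protocol does not describe, and a reader who relies on Table 5-1 will not learn of it.

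The omitted term is one of the two stratification variables (Protocol 5.4, SAP 3.2). If a stratifying variable is prognostic and is left out, the analysis ignores balance that the design created. The estimate stays unbiased, but its standard error is overstated and the test becomes conservative.

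There is also a loss of comparability. Abutment BI would be adjusted for different factors from whole-mouth BI and from abutment bleeding sites, the two results it would naturally be read against.

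**Working it through.** **1. Which model the protocol requires.** The rule in 12.2.8 points to the primary or secondary analysis. For BI the primary model is at Week 12 (12.2.5) and the secondary is at Week 6 (12.2.6.5, same model). Both contain baseline MGI (low, high), so either reading of the rule gives the same answer. The requirement is by reference; 12.2.8 does not name the factor for this endpoint.

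**2. How the SAP treats the factor elsewhere.** The sections covering an ANCOVA for an endpoint other than MGI are:

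- primary and secondary: 4.4.1.2, 4.5.1.1 and 4.5.1.3 to 4.5.1.9, which is 9 sections
- exploratory: 4.5.2.2, 4.5.2.3 and 4.5.2.5 to 4.5.2.9, which is 7 sections

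That makes 9 + 7 = 16. Fourteen list the factor explicitly, one (4.5.1.5, BI at Week 6) takes it by reference to the primary model, and one (4.5.2.2) omits it.

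**3. Whether a reason is available.** The SAP drops the factor for MGI (4.5.1.2 and 4.5.2.4) and says why: baseline MGI is the covariate. In 4.5.2.2 the covariate is BI, so that reason does not carry over. The wording of 4.5.2.2 follows the pattern of the MGI model, "treatment group, gender and denture material type (acrylic or cobalt chrome) factors and the baseline MGI score as a covariate", rather than that of the other BI sections. A copying slip is therefore likely, but this is inference.

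**4. Whether the change is recorded.** Table 5-1 covers proportionate reduction, repeatability populations, medication listings, COVID-19 safety outputs and missing data. The row that cites SAP 4.5.2 concerns proportionate reduction only. No row mentions model factors.

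**5. Size of the effect (illustration).** The documents give no figure to reproduce here. Inputs: 128 evaluable subjects (Protocol 12.1); two-sided alpha 0.05, which the protocol states for the primary endpoint; R², the share of residual variance explained by the MGI stratum after the other terms, **assumed**; and, for the power column, an **assumed** 80% power with the factor included.

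- SE ratio, omitted to included = 1/√(1 − R²)
- Equivalent loss of subjects = 128 × R²
- True alpha when omitted = 2[1 − Φ(1.960/√(1 − R²))]
- Power when omitted = Φ(1.960 + 0.842 − 1.960/√(1 − R²))

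| Assumed R² | SE ratio | Equivalent loss of 128 | True alpha | Power |
|---|---|---|---|---|
| 0% | 1.000 | 0 | 0.0500 | 80.0% |
| 1% | 1.005 | 1.3 | 0.0489 | 79.7% |
| 5% | 1.026 | 6.4 | 0.0443 | 78.5% |
| 10% | 1.054 | 12.8 | 0.0388 | 76.9% |

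A simulation with no treatment effect (6,000 runs per R², n = 128, 1:1 allocation balanced within four strata assumed to be of about equal size) gave rejection rates without the factor of 0.051, 0.047, 0.045 and 0.041, and with it of 0.051, 0.049, 0.052 and 0.050. The Monte Carlo standard error is √(0.05 × 0.95/6000) = 0.0028, so these agree with the formula. The mean estimated difference was within 0.004 of zero throughout, so there is no sign of bias.

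**6. Cost of including the factor.** The SAP model has 5 parameters (intercept, treatment, gender, material, baseline BI), leaving 128 − 5 = 123 residual df. With the stratum there are 6, leaving 122. The critical t moves from 1.9794 to 1.9796.

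**The case against.** The strongest reply is that this does not matter much. Study success rests on whole-mouth BI at Week 12, whose model agrees in both documents. Abutment BI is exploratory, and the omission cannot inflate type I error. All of that stands.

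A second reply is that the SAP is not ambiguous. The protocol leaves further analysis detail to it, 4.5.2.2 gives one explicit model, 4.5.2 promises only similarity, and the factor rule in SAP 3.2 is stated for primary and secondary analyses. This is also fair: a programmer working from the SAP has a single instruction. It does not answer the point, because that instruction departs from a protocol rule that says the model is the same, and the table meant to hold such departures is silent.

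Third, the R² values are assumed. Eligibility confines baseline mean MGI to 1.75 to 2.30, the stratum only splits that 0.55-point range at 2.0, and the model already adjusts for baseline abutment BI. The 5% and 10% rows are therefore a range, not a forecast, and the true effect may be close to the 0% row.

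**Conclusion.** The point holds. SAP 4.5.2.2 omits a stratification factor that Protocol 12.2.8 requires by reference, gives no reason, and is the only non-MGI model in the SAP to do so. Table 5-1 does not disclose the change. This follows from the text alone and does not depend on the assumed R² values.

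The statistical consequence is minor and confined to two exploratory models, abutment BI at Weeks 6 and 12. It ranges from nothing to a modest loss of precision: a 5.4% larger standard error if the stratum explained 10% of residual variance. Any error is in the conservative direction. The main reason to correct it is traceability between protocol and SAP, together with consistent adjustment across the BI-based endpoints. It should be corrected, but it does not threaten the trial's conclusions.

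**What to change.** In SAP 4.5.2.2, add baseline mean overall MGI (low, high) to the factors, next to treatment group, gender and denture material type. Keep baseline abutment BI as the covariate. The section then matches Protocol 12.2.8, the whole-mouth BI model and the abutment bleeding-sites model.

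If the omission was deliberate, leave the model as it is and add a row to Table 5-1 that states the change and the reason.

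Either step should be taken before database lock and unblinding, so that results cannot influence the choice. The cost is one phrase, or one table row. Adding the factor uses one residual degree of freedom in each of two models and needs no new data.
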